#### 4.1 Inclusion-exclusion criteria

#### 4.1.1 Inclusion criteria

- 1. A case is defined as a patient who;
  - a. had a *C. difficile* toxin positive (gold standard method CCNA) stool sample
  - b. had a *C. difficile* toxin positive (new novel method –SIMOA) stool sample
  - c. had a free toxin negative stool sample but was positive for a cytotoxigenic strain (by culture or detection of toxin gene)
- 2. A Control is defined as a patient who had a sample included int eh sample collection study but tested negative by all assays

#### 4.1.2 Exclusion criteria

- 1. Patients outside of the COMBACTE-CDI sample collection study
- 2. Patients with a GDH positive/toxin negative sample during the sample collection study

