Appendix 1. Variable description table

## 1. Introduction

This statistical analysis plan (SAP) is to provide a description of the study design, study variables, and statistical analysis methods for the COMBACTE-CDI study, which aims to develop a detailed understanding of the epidemiology and clinical impact of CDI. More specifically, this project's objectives are to:

- Align and understand the unmet public health needs relating to CDI;
- Identify and quantify the direct and long-term burden of CDI on healthcare systems

The COMBACTE CDI case/control studyfollows a cohort of patients identified during the COMBACTE CDI sample collection study. The sample collection study involved 119 sites from 12 countries from Europe, with a national coordinator recruited for every country. National coordinators selected participating sites (PS) to cover all major geographical regions within every country. Participating sites were recruited at a rate of one per 3 million population in all study countries. Figure 1 shows the full study design.

Figure 1. Schematic representation of study design (WP1 &WP2). A synergistic approach will enable completion of all the objectives from WP1 and WP2, with data created from a single, large complex study flowing into other objectives for further results analysis. Boxes in blue denote objectives in WP1, and those in orange denote for objectives in WP2. Due to the inter-related nature of the

objectives within both WP1 and WP2, the flow of work has been planned to ensure maximum outputs within the timeframe of the grant. The directions of the arrows indicates data flow and, therefore, also the timing of activities; i.e. Strains cannot be analysed (1.2) until after they have been collected (1.1). This ambitious comprehensive project design takes influence from several existing, separate studies; the scope of producing all of these is data from one, well-designed and far-reaching study is novel and innovative.

During the COMBACTE-CDI sample collection study, cases and controls were identified; Multiple diagnostic definitions of a case;

- Case defined as C. difficile toxin positive (gold standard method CCNA) positive
- Case defined as C. difficile toxin positive (new novel method –SIMOA)
- Case defined as free toxin negative but positive for a cytotoxigenic strain (by culture or detection of toxin gene)
- Control defined as negative by all assays

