## 2.1 Selection of case and controls (total possible to be recruited)

		Location	of participant a sample	at time of
Diagnostic categories:		Hospital	Community	TOTAL
CDI positive cases	1. CCNA positive	83	20	103
	2. CCNA negative/Simoa positive	49	22	71
	3. CCNA and Simoa negative but CTC positive or bioFire pos	24	15	39
CDI negative controls	4. Negative control *	365	147	512
Total number selected for case/control study 521 204		725		

Table1. The total number of samples selected for the case/control study (n=725). The table shows the number of CDI positive cases according to the indicated diagnostic categories (1-3, n=213) and by location of participant (Hospital n=156, Community n=57). Negative controls (4, n=512) were selected at a rate of 1:3 from matching participating sites (one case to three controls). As some participating sites had less than 3 controls per case, average rate was of 1:2.4 (one case to 2.4 controls) (\*).

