#### 2.5. Analysis objectives

The main objectives of the analyses are to;

- 1. Determine the outcomes of cases (of each classification) vs controls, and compare between countries and hospital vs community cases
- 2. Determine the risk factors for cases (of each classification) vs controls, and compare between countries and hospital vs community cases

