## 6. Outcome and key variables

#### 6.1. Outcome

The outcome CDI is defined as either;

- 1. a diarrhoeal sample that is *C. difficile* toxin positive using the gold standard method CCNA
- 2. a diarrhoeal sample that is *C. difficile* toxin positive using a new novel method (SIMOA)
- 3. a diarrhoeal sample that is positive for a toxigenic isolates of *C. difficile* (by either cytotoxigenic culture of toxin gene testing) AND is negative for free toxin

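### SAP 4.1.2 excludes GDH-positive, toxin-negative patients study-wide without naming the toxin assay, which contradicts case definition 1c

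*SAP*

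**What the plan says.** SAP 4.1.2 has two exclusions. The first removes patients from outside the sample collection study. The second removes "Patients with a GDH positive/toxin negative sample during the sample collection study". Both stand under the general inclusion-exclusion heading, and neither is restricted to cases or to controls.

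SAP 4.1.1 defines three kinds of case. Definition 1a is CCNA toxin positive and 1b is Simoa toxin positive. Definition 1c is a patient who "had a free toxin negative stool sample but was positive for a cytotoxigenic strain (by culture or detection of toxin gene"). The Introduction lists the same three. Section 6.1 repeats the third as an outcome definition, a toxigenic isolate in a sample that "AND is negative for free toxin". Table 1 in SAP 2.1 shows the group as category 3, "CCNA and Simoa negative but CTC positive or bioFire pos", with 39 patients.

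On the other side, the Introduction has "Control defined as negative by all assays", and 4.1.1 says the same. The first analysis objective in SAP 2.5 is to "Determine the outcomes of cases (of each classification) vs controls"; the second makes the same comparison for risk factors.

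**The concern.** A GDH-positive patient who meets definition 1c satisfies an inclusion criterion and an exclusion criterion through the same test result. The SAP gives no order of precedence, so two analysts following it could build different case sets.

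The missing assay name makes this worse. The study measures toxin in three ways: the GDH/toxin kit and CCNA at the coordinating laboratory, and Simoa (all in protocol 3.1.4). Exclusion 2 does not say which of them makes a sample toxin negative.

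At stake is mainly the comparison by diagnostic type. The SAP's stated purpose is to describe severity, risk factors and outcomes for the different diagnostic types, and free-toxin-negative carriage of a toxigenic strain is one of them. Read literally, the exclusion could remove that group.

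**Working it through.** **1. Reproduce Table 1 (SAP 2.1).**

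- Hospital cases: 83 + 49 + 24 = 156
- Community cases: 20 + 22 + 15 = 57
- All cases: 103 + 71 + 39 = 213
- Controls: 365 + 147 = 512
- Total: 213 + 512 = 725
- Controls per case: 512 / 213 = 2.40

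All agree with the SAP.

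**2. Whom does exclusion 2 cover?** It sits beside exclusion 1, which must apply to cases and controls alike. Where the SAP wants a rule for controls only, it says so: the 8-week rule in 4.1.5 is expressly confined to the control cohort. Exclusion 2 has no such limit, so on its face it is study-wide.

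**3. What does toxin negative mean?**

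- *The SAP's own usage.* Definition 1b and section 6.1 item 2 call a Simoa-positive sample toxin positive, and definition 1a and item 1 do the same for CCNA. Category 3 is the group negative by both. In the SAP's terms, toxin negative therefore means CCNA negative and Simoa negative.
- *The kit.* Protocol 3.1.4 uses a combined GDH/toxin test, and protocol 3.2.3.1 defines a case by the pair GDH positive and toxin positive. Exclusion 2 mirrors that pairing, so a kit reading is possible.

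**4. Size under the SAP's own usage.** The exclusion reaches the GDH-positive members of category 3. Let g be the unknown share of the 39 who are GDH positive. Cases removed = 39g and cases left = 213 − 39g. GDH results by category are not given, so g lies anywhere from 0 to 1. At the upper limit, g = 1:

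- All cases: 39 / 213 = 18.3%, leaving 213 − 39 = 174
- Hospital: 24 / 156 = 15.4%, leaving 132
- Community: 15 / 57 = 26.3%, leaving 42
- Category 3: 39 − 39 = 0

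At g = 0 nothing is removed and all 213 stay.

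**5. Size under the kit reading.** Any case that was GDH positive but kit-toxin negative would be caught, including cases positive by CCNA or Simoa. Neither document cross-tabulates the kit result against the case categories, so no count can be given.

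**6. Was the rule applied at selection?** The caption calls its counts "The total number of samples selected for the case/control study (n=725"), and the 39 in category 3 are among them. The rule was evidently not applied to that group at selection. But the heading of SAP 2.1 describes the total possible to be recruited, so the table does not define the final analysis set.

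**The case against.** The best defence is that the intent is clear. The Introduction, 4.1.1, 6.1 and Table 1 all make the free-toxin-negative, toxigenic group a case group, and only one line conflicts. A sensible analyst would keep the 39. There is also a coherent purpose for the line: a GDH-positive sample that meets none of 1a to 1c is not a case, and it is not a clean control either, so it belongs in neither group.

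Much of this stands. It makes it likely that the conflict is one of wording, and it rules out any claim that the study has already gone wrong. It does not remove the contradiction, because the SAP never states that purpose. A second explanation is equally open: the line may be left over from the protocol, where a case had to be both GDH positive and toxin positive. The documents do not show which is right. Reading the line as a rule for controls is no way out either. It is not worded that way, and if all assays includes GDH it would add nothing to the control definition.

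A reader might go further and infer that category 2, "CCNA negative/Simoa positive", is caught as well, by taking toxin negative to mean CCNA negative alone. The documents do not support that: the SAP expressly calls Simoa-positive samples toxin positive.

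**Conclusion.** The contradiction is real, and no other part of the SAP or protocol resolves it. In the SAP's own terms, exclusion 2 could remove at most 39 of 213 cases (18%) and could empty one of the three case classifications. That bound assumes that all 39 are GDH positive, which the documents neither state nor deny. Under the kit reading other categories could be affected, by an amount that cannot be counted.

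Two stronger conclusions should not be drawn. A reader might infer that cases were lost; Table 1 shows category 3 among those selected, so the fault lies in the rule for building the analysis set.

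A reader might also take the 8-week rule in SAP 4.1.5 as a second error. It applies to controls only, so the crude comparison of CDI history is not symmetric and should be interpreted with that in mind. But removing possibly misclassified controls is a legitimate aim, and the size of any distortion depends on how much previous CDI falls within 8 weeks of the index sample, which the documents do not give.

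**What to change.** Reconcile SAP 4.1.2 with 4.1.1 and 6.1 so that no patient meeting 1a, 1b or 1c is excluded. Either of two edits would do this:

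- limit exclusion 2 to GDH-positive samples that meet none of 1a to 1c, and state that these patients are neither cases nor controls; or
- delete exclusion 2, if the sponsor confirms that it was carried over from the protocol's case definition.

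If any exclusion based on toxin is kept, name the assay. The cost is SAP wording only: no new data are needed, and all 213 selected cases remain eligible under this criterion. When CDI history is reported, a one-line reminder that the 8-week rule applied to controls only would be enough.

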#### 4.1.5 Definition of controls

Patients with CDI positive samples within the 8 weeks previous or subsequent to the Index sample date will be excluded from the control cohort, after receipt of the CRF. The target case/control ratio is 1:3, though there may be variability in this ratio due to site sample size.

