#### 3.2.3 Sampling criteria for case/control studies (objectives 1.3)

#### 3.2.3.1 Inclusion criteria

The study will collect data on cases/controls identified during the sample collection study (section 3.1 above)

- 1. Any patient who had a sample sent to the European coordinating laboratory and was positive for CDI (GDH positive/toxin positive) at the European coordinating laboratory
- 2. A matched (age/gender) patient from the same participating site as a patient in criteria 1, but that had a negative result for CDI at the European Coordinating Laboratory.

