#### 3.2.7 Data analysis

Comparisons will be made between recurrence/Morbidity/Mortality (crude and attributable) rates in different healthcare settings and countries. Outcomes will also be compared for different strain types (as identified in O1.2).

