## 6.3. Study period and important time points.

The study period is June 2018-June 2019.

The index date for the cases is defined as the date of the stool sample collection (either June/July 2018 or Oct/Nov 2019).

The index date for the controls is defined as the date of the stool sample collection either June/July 2018 or Oct/Nov 2019).

Queries within the CRF relate to that patients episode, with reference to the six months prior and six months subsequent to the index sample.

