2.7	Did the patient receive any supportive measures/domestic help by friends or relatives during the presence of CDI?	Binary	Univariate/multivariate	Patient admission when the sample was taken

2.7.1	If yes, how many hours per day?	Continuous	Univariate/multivariate	Patient admission when the sample
				was taken
2.8	Did the patient receive any supportive measures/domestic help by professionals during the presence of CDI?	Binary	Univariate/multivariate	Patient admission when the sample was taken
2.8.1	If yes, how many hours per day?	Continuous	Univariate/multivariate	Patient admission when the sample was taken
2.9	Were any CDI related purchases necessary?	Binary	Univariate/multivariate	Patient admission when the sample was taken
2.9.1	If yes, please describe below	Categorical	Univariate/multivariate	Patient admission when the sample was taken
3. Laborat	ory Testing	1	1	
3.1	Did the patient have any test for other enteric pathogens up to 7 days before or up to 7 days after the EUCLID sample was taken	Binary	Univariate/multivariate	Patient admission when the sample was taken
3.1.1	If yes please indicate test results	Categorical	Univariate/multivariate	Patient admission when the sample was taken
3.2	What was the local policy for repeat testing of patients with CDI (at the time of the sample)	Binary (repeat or not repeat)	Univariate/multivariate	Patient admission when the sample was taken
4. CDI Test	ting	ſ	ſ	
4.1	Was the patient tested for CDI due to diarrhoea in the 6 months before the index sample	Binary	Univariate	Up to 6 months previous to the sample
4.1.1	If yes, date of sample and result of tests	Number of days between sample and	Univariate	Up to 6 months previous to the sample

		test is		
		Continuous		
		Decult of		
		Result of		
		Catagorical		
12	Did the nationt	Rinary	Univariato	Up to 6 months
4.2	have a diarrhoea	binary	Univariate	after the sample
	enisode in the 6			arter the sumple
	months following			
	the index sample			
4.3	Was the patient	Binary	Univariate	Up to 6 months
	tested for CDI in the	,		after the sample
	6 months following			
	the index sample			
4.3.1	If yes, date of	Number of	Univariate	Up to 6 months
	sample and result	days		after the sample
	of tests	between		
		sample and		
		test is		
		Continuous		
		Result of		
		test is		
		Categorical		
4.4	Was the Clostridium	Binary	Univariate	Patient admission
	difficile sent for	,		when the sample
	ribotyping?			was taken
4.5	Was the severity of	Binary	Univariate	Patient admission

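### Controls, but not cases, are removed for a CDI-positive sample in the 8 weeks after the index date, which inflates the case-control odds ratio for later CDI positivity

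*SAP*

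**What the plan says.** SAP 4.1.5 sets the rule: "Patients with CDI positive samples within the 8 weeks previous or subsequent to the Index sample date will be excluded from the control cohort". It is applied "after receipt of the CRF", and SAP 6.3 says the CRF questions are framed "with reference to the six months prior and six months subsequent to the index sample". Membership of the control group is therefore settled when up to six months of follow-up are on paper.

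Neither of the other control definitions looks ahead. SAP 4.1.1 takes a patient in the sample collection study who "tested negative by all assays". Protocol 3.2.3.1 takes a matched patient "that had a negative result for CDI at the European Coordinating Laboratory", and Protocol 3.2.3.2 lists no exclusions. Nothing in SAP 4.1 removes a case for a later positive sample.

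The first analysis objective in SAP 2.5 is to "Determine the outcomes of cases (of each classification) vs controls". Appendix 1 item 4.3 records whether the patient was "tested for CDI in the" six months after the index sample. Item 4.3.1 records the dates and results of those tests. Both are marked for univariate analysis, which SAP 7.2 describes as covering outcomes as well as risk factors, with categorical variables compared between cases and controls.

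**The concern.** The forward half of the rule selects controls on an event that happens during follow-up, and a positive result in item 4.3.1 is that same event. A control must stay free of a recorded positive for 8 weeks to remain in the analysis, while a case need not. The comparison of later CDI positivity is then unequal by design. Control positives in the first 8 weeks disappear with the patients who had them, and case positives in the same weeks are counted. For this outcome the bias runs one way: it exaggerates the excess in cases. No planned analysis would reveal it, because the only sensitivity analysis mentioned (SAP 5) concerns missing data.

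The backward half of the rule, which concerns CDI history, is a separate matter and is not at issue here.

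**Working it through.** **Inputs from the documents.** Exclusion window after index: 8 weeks (SAP 4.1.5). Follow-up: 6 months, about 26 weeks (SAP 6.3). Selected: 213 cases and 512 controls (SAP 2.1, Table 1). The ratio is 512/213 = 2.40, which reproduces the stated 1:2.4. Table 1 gives the total available, and the exclusion acts on CRFs returned later.

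**Inputs not in the documents (assumed).** The 6-month risk R of a recorded positive in controls, and the fraction f of those control patients whose first positive falls in the first 8 weeks.

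**Share of follow-up closed off.** 8/26 = 30.8%. In days, 56/183 = 30.6%.

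**Effect on the odds ratio.** The rule removes a proportion fR of controls, all of them later positives.

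- Retained risk = (R - fR)/(1 - fR).
- Retained odds = R(1 - f)/(1 - R), which is the true odds times (1 - f).
- The case odds are unchanged, so the case-control odds ratio is multiplied by 1/(1 - f). This factor depends on R and on the case risk only through f.

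**Illustration (assumed R = 4% in controls, 15% in cases).** True odds ratio = (0.15/0.85)/(0.04/0.96) = 4.24. For the even spread, a constant hazard gives an 8-week risk of 1 - 0.96^(8/26) = 1.25%, so f = 0.0125/0.04 = 0.31.

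| Timing of control positives | f | Controls removed (of 512) | Retained control risk | Odds ratio | Inflation |
|---|---|---|---|---|---|
| Even (constant hazard) | 0.31 | 6 | 2.8% | 6.2 | 1.45 |
| Half early | 0.50 | 10 | 2.0% | 8.5 | 2.0 |
| 60% early | 0.60 | 12 | 1.6% | 10.6 | 2.5 |

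With R from 3% to 5% and f from 0.5 to 0.6, the number removed runs from 512 x 0.03 x 0.5 = 7.7 to 512 x 0.05 x 0.6 = 15.4.

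**No true difference.** Give cases and controls the same 6-month risk and a constant hazard. For risks of 2% to 20% the rule alone produces an apparent odds ratio of 1.45 to 1.50. At 5%, controls appear to have 3.5%; at 10%, 7.0%. With all 213 cases pooled, a two-sided 5% level and the normal approximation, a false significant difference would be found about 17% and 28% of the time respectively.

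**What is and is not forced to zero.** Only a positive result within 8 weeks, as recorded in item 4.3.1, is impossible in a retained control. A diarrhoea episode (item 4.2), a test with a negative result (item 4.3) and undetected CDI can all still occur.

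**The case against.** The best defence is that the rule guards against index false negatives. Protocol 1.4.2 warns that toxin degrades if testing is delayed, and samples travel to a single laboratory. A positive soon after a negative index sample may be a missed index case, and keeping that patient as a control could pull risk-factor odds ratios toward the null. This stands for objective 2, although the SAP does not give it as the reason, and controls must also be negative by culture and toxin gene detection as well as for toxin. It does not stand for objective 1, where the excluded event is itself compared.

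The second defence is that the affected comparison is not a headline one. The primary outcome in Protocol 3.2.2 is crude mortality at 30 days and 6 months. Protocol 3.2.7 states the recurrence analysis as "Comparisons will be made between recurrence/Morbidity/Mortality (crude and attributable) rates in different healthcare settings and countries", which does not name cases against controls. Item 4.3.1 sits under CDI testing rather than in the outcomes section of Appendix 1. That limits the importance of the point, but SAP 7.2 would still compare the item by case status.

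A reader might go further and infer that the rule overstates the case excess in death and readmission. The documents do not support that. Controls who die early without a positive sample stay in, and those who survive to test positive leave, which by itself would raise control mortality. The net direction depends on the prognosis of the removed controls, which is not given.

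**Conclusion.** The point holds for one comparison: later recorded CDI positivity, cases against controls, under objective 1. Positivity in controls is zero by construction for about 31% of follow-up. The odds ratio is inflated by 1/(1 - f), about 1.45 with evenly spread events and 2.0 to 2.5 if 50-60% are early. The direction and the formula follow from the rule. The values of f and R are assumptions, because the documents give no rate of later positives in controls.

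The effect on mortality and readmission is probably small, since few controls are likely to be removed, and its sign is unsettled. It would also be too strong to infer that the forward exclusion is wrong for the risk-factor analysis. There it trades possible misclassification at index against conditioning on the future, and either choice can be defended if both results are shown. The point is worth correcting but does not threaten the primary outcome.

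**What to change.** Amend SAP 4.1.5 to separate the two objectives.

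- **Outcome comparisons (objective 1):** define a control by the index sample alone, negative by all assays as in SAP 4.1.1. Count later positive samples as outcomes. Apply the forward 8-week exclusion only as a sensitivity analysis.
- **Risk factors (objective 2):** the forward exclusion may stay as a guard against false-negative index samples, provided the SAP gives that reason and results are also reported without it.
- **Both:** report how many controls the forward rule removes, by country and by hospital or community setting.

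The cost is a short edit and a second run of some tables. No new data are needed, because the rule already works from returned CRFs. Controls are also preserved when the achieved ratio is 1:2.4 against a target of 1:3. The downside is that a few retained controls may be missed index cases, which the sensitivity analysis addresses.
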